10.3 Clinical Laboratory Assessments

Blood and/or urine samples will be collected as indicated in the schedule of assessments (Fig.1). It is preferable to collect the clinical laboratory samples from each subject at a consistent time of day throughout the trial, and to recommend that the subject have a similar diet, avoiding variation in protein intake (especially cooked meat protein), and exercise pattern during these periods, in order to reduce variability in the samples over time.

Liver panels will be analyzed monthly during the unblind, treatment period using both central and local labs, as needed, and per standard of care according to the subject's individual medical needs.

Serum pregnancy testing and Blood venous gas-analysis will be performed locally during screening period and then during every scheduled visit.

10.4 Physical Examination and Vital Signs

A full physical examination will be performed and documented during every visit and during End of Treatment visit. Any changes in medication or AEs will be recorded in the eCRF. Body weight will be taken post-void. It is preferable to use the same scale for each measurement.

The investigator or his/her appointed designee is primarily responsible to perform the physical examination. If the appointed designee is to perform the physical examination, he/she must be permitted to do so by local regulations and his/her name must be included on any globally and locally required documents.

Whenever possible, the same individual should perform all physical examinations. Any undesirable condition present at a post-treatment physical examination that was not present at the baseline examination should be documented as an AE and followed to a satisfactory conclusion.

Vital sign data, including seated blood pressure, heart rate, temperature, height, and weight, will be taken at the visits identified in the Schedule of Assessments.

10.5 Assessment of Liver Symptoms, Signs or Test Abnormalities

Testing for hepatic transaminase (ALT/AST), alkaline phosphatase, and BT will be performed during screening visits. Testing for hepatic transaminase (ALT/AST) will be performed during run-in and at each monthly visit in the tolvaptan arm, whereas it will be performed during three monthly visits in the metformin arm.

10.5.1 Requirements for Repeated Liver Testing

10.5.1.1 Repeated Liver Testing in Subjects with Normal Values at Screening

The appearance of any suspicious symptom or sign should trigger prompt testing of hepatic function (i.e., within 72 hours). Local laboratory testing is acceptable, ideally with a concurrent central laboratory sample for confirmation.

Any transaminase or bilirubin values which exceed 2 x ULN should also prompt immediate retesting within 72 hours. While values remain in an abnormal range, testing frequency should be increased to at least weekly for the first month, gradually returning to monthly/three monthly as indicated by the results.

Subjects exhibiting such an increase during the tolvaptan titration/run-in phases will be disqualified from randomization on safety grounds and should not be randomized.

Should the cause of the abnormality be determined to be unrelated to tolvaptan exposure (e.g., having identified a plausible alternative explanation) such a subject may be rescreened only with medical monitor approval.

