Randomization visit will occur on Day -29. During this visit patients will be randomized (in a ratio 1:1 tolvaptan:metformin) to each arm of treatment and will start an **IMP titration period** (3 weeks from -28 to -8). Subjects not tolerating the minimum IMP dose will be considered "Titration failures" and will complete End of Treatment (EoTx) visit assessments and will be followed up after 7 days by phone call to assess any ongoing AEs. Subjects tolerating the minimum IMP dose enter the unblind **run-in period** (1 week from Day -7 to -1). During the "Run-in" phase, subjects will continue on a stable IMP dose to confirm tolerability over a longer period. At the end of the run-in period (Day -1), subjects not tolerating the minimum IMP dose will be considered "Run-in failures" and will complete EoTx visit assessments and will be followed up after 7 days by phone call to assess any ongoing AEs. Subjects completing the run-in will start the open-label **24 months treatment period**, during which visits will be collected three-monthly. At the end of the 24th month, and in case of early treatment cessation, **follow-up period** (3 weeks from +8 to +21) will start, during which 2 visits have to be collected. No IMP will be administered during this period.

Assessments at the Randomization (Day -29), End of IMP Run-in Period (Day -1), End of each three-monthly of on-therapy period will include those for points 2 to 8 of screening period plus IMP dispensation.

Assessments during EoTx Visits (in case of Titration failure, Run-in failure, early treatment cessation) and Follow-up visits will include those for points 2 to 8 of screening period. Non contrast enhanced CT-scan of the kidneys for TKV measurement will be also performed at the end of Month 24.

Patients treated with tolvaptan, will anyhow undergo monthly visits during the first 18 months of therapy (as prescribed by the additional monitoring requested by AIFA), then every three months.

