4.1 Screening Period (up to Day -30)

No investigational treatments will be administered during the screening period.

Preliminary eligibility for the trial will be initially assessed using the subjects' historical laboratory or imaging data.

During this period, the subject's eligibility for the trial will be confirmed using historical genetic test data and imaging data of the kidneys to support a diagnosis of ADPKD and to verify the level of CKD primarily due to ADPKD and not to other renal (hypoplasia) or metabolic (diabetic or hypertensive nephropathy) disorders.

Eligibility will be confirmed by the mean of eGFR calculated from the subjects' 2 pretreatment, central-lab, serum creatinine assessments (collected at least 24 hours apart). The final screening visit on Day -29 will not be scheduled until laboratory results from the second screening visit (V2) are received and evaluated. The eGFR values will be estimated based on the Chronic Kidney Disease-Epidemiology (CKD-EPI) formula. Subjects will be told that they will receive tolvaptan or metformin during the subsequent periods of the trial.

On Day -30, patients will undergo TKV measurement by means of Ct- or MRI-scan (if not already performed within the 6 months before the enrollment). Then, patients will be randomized to receive either metformin or tolvaptan and they will be told to start IMP assumption since the day after randomization.

Those randomized in metfromin arm will receive Zuglimet® 500 mg (2 packages, each of them containing 3 blisters; every blister contains ten 500 mg coated tablets).

Those randomized to tolvaptan arm will receive Jinarc® 45/15 mg (2 packages, each of them containing 4 blisters; every blister contains seven 15 mg tablets of and seven 45 mg tablets).

The screening period will last 1-2 weeks, but may be extended up to an additional 8 weeks for subjects who require modification of medical care or further medical evaluation specifically for this trial. This may include, for example, stabilizing anti-hypertensive regimens for subjects discontinuing diuretics or "wash-out" of other investigational agents.

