4.3 IMP Titration Period (since Day -28 up to Day -8)

Subjects randomized in tolvaptan arm will be given a split dose of 45/15 mg tolvaptan (unblind) with upward titration every 7 days to 45/15 mg, 60/30 mg, up to a maximum dose

of 90/30 mg per day over 3 weeks. Jinarc® has to be taken between meals; the first dose upon waking and the second dose after eight hours from the first.

Dose up-titration will be done after tolerability check (by phone call the patient will be asked: "Are you having troubles taking this drug? Are you able to tolerate this dose for the rest of your life?"). Up-titration will be done the day after tolerability check, in Day -22 and in Day -15.

Subjects who are unable to tolerate at least 45/15 mg of daily tolvaptan will be considered "Run-in failures" and will complete an EoTx visit and be followed up after 7 days by phone call to assess any ongoing AEs.

Subjects randomized to metformin arm will be given a single dose of 500 mg of metformin for the first week (unblind), then a split dose of 500/500 mg metformin with upward titration after 7 days to 500/500/500 mg, (that is the maximum trial dose of metformin per day). Zuglimet® has to be taken between meals; the first dose upon waking, the second and the third daily dose after eight hours from the previous dose.

Dose up-titration will be done after tolerability check (by phone call the patient will be asked: "Are you having troubles taking this drug? Are you able to tolerate this dose for the rest of your life?"). Up-titration will be done the day after tolerability check, in Day -22 and in Day -15.

Subjects who are unable to tolerate at least 500/500 mg of daily metformim will be considered "Run-in failures" and will complete an EoTx visit and be followed up after 7 days by phone call to assess any ongoing AEs. Subjects tolerating the minimum IMP dose will enter the unblind run-in period (1 week from Day -7 to -1).

Assessments during up-titration phone call will include:

1) Assess IMP tolerability

2) Assess AEs, if reported

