10.5.1.2 Repeated Liver Testing in Subjects with Abnormal Values at Screening

Subjects found to have liver laboratory abnormalities at screening or who have a history of non-ADPKD-related liver disease will require further evaluation. These subjects will need to have the special liver eCRF completed and additional testing will be required during screening (to confirm the stability of the abnormality) and during the tolvaptan run-in phase at least 1 week prior to randomization (to confirm eligibility for randomization).

Management of such subjects should be closely coordinated with the trial's Medical Monitor. In these subjects, further changes in liver test levels of > 2 x upper limit of their highest screening value at any point post-screening should prompt re-testing within 72 hours. Should such increase occur in the tolvaptan titration/run-in phase, the subject will be disqualified from trial.

10.5.1.3 Liver Test Abnormalities and Interruption/Discontinuation of Investigational Medicinal Product

Liver transaminase or bilirubin levels reaching or exceeding 2 x ULN that have an uncertain or rapidly increasing trajectory should prompt at least temporary IMP interruption. IMP should not be resumed until monitoring indicates abnormalities have resolved, are stable or are not rapidly increasing, and then only with an increased frequency of monitoring.

Subjects would not typically be allowed to resume treatment with IMP if they have:

- transaminase levels rise above 8 x ULN;
- transaminase levels are > 5 x ULN for more than 2 weeks; or
- concurrent elevations of transaminase > 3 x ULN and BT > 2 x ULN.

Subjects with these levels of abnormality may be re-challenged with IMP if abnormalities were adjudicated as having a < 50% likelihood of being related to IMP (per DILI network [DILIN] probability criteria) by the investigator and medical monitor.

All elevations will be assessed by the medical monitoring team. The subject must also be willing to comply with these monitoring measures, be informed of the potential risks, and consent to IMP re-challenge.

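### The tolvaptan titration/run-in liver rule is written as a bar to randomisation, but it applies to patients already allocated, and their short follow-up conflicts with the all-randomised analysis

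*Combined protocol and SAP*

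**What the plan says.** Liver rules:

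- Section 10.5.1.1 covers patients with normal screening values. After a rise above 2 x ULN in tolvaptan titration or run-in, they "will be disqualified from randomization on safety grounds and should not be randomized". If the cause is judged unrelated to tolvaptan, "such a subject may be rescreened only with medical monitor approval".
- Section 10.5.1.2 covers patients with abnormal screening values. It asks for extra liver testing "during the tolvaptan run-in phase at least 1 week prior to randomization (to confirm eligibility for randomization"). The trigger is a rise above twice their highest screening value, and the consequence is: "Should such increase occur in the tolvaptan titration/run-in phase, the subject will be disqualified from trial".
- Section 10.5.1.3 covers drug in either arm. At 2 x ULN or more with an uncertain or rapidly rising course, treatment is at least interrupted, and "IMP should not be resumed until monitoring indicates abnormalities have resolved, are stable or are not rapidly increasing".

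Timing:

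- Section 4: "Randomization visit will occur on Day -29". The heading of section 4.2 says Day -30.
- Section 4.1: once patients are randomised, "they will be told to start IMP assumption since the day after randomization".
- Section 4.3, for titration from Day -28 to Day -8: "Subjects randomized in tolvaptan arm will be given a split dose of 45/15 mg tolvaptan".
- Section 4.4 puts run-in at Day -7 to Day -1. Section 4.7 puts the last scheduled treatment 25 months after randomisation.

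Analysis: section 12.3 specifies intention-to-treat in all randomised subjects, using linear mixed-effects models among other standard methods, and ignores missing data.

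**The concern.** The liver rules fit a design in which everyone takes tolvaptan in a run-in and is randomised afterwards. Here allocation comes first, so a patient who meets the rule is already a randomised member of the tolvaptan arm.

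Two things follow. First, a drug effect arising after allocation ends participation in one arm only. A metformin patient with the same rise is retested and may have drug interrupted, but is not disqualified. Second, if follow-up ends soon after the rise, the patient stays in the intention-to-treat set in name but gives only a few weeks of creatinine to a two-year slope: two screening values, end of run-in if reached, and the end-of-treatment visit. Ignoring missing data does nothing to make up for the rest.

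**Working it through.** **1. Does allocation precede titration and run-in?** Section 4.7 gives a figure that can be checked. Months last 28 days (section 7.1.3).

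- Titration, Day -28 to Day -8: 21 days
- Run-in, Day -7 to Day -1: 7 days
- Main treatment period: 24 x 28 = 672 days
- Total: (21 + 7 + 672) / 28 = 700 / 28 = 25.0 months

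The stated 25 months is reproduced only if titration and run-in follow randomisation. Randomisation at Day 0 would give 672 / 28 = 24 months. Sections 4.4, 4.8, 10.2 and 11 also contain wording that puts randomisation later, but titration by allocated arm in section 4.3 rules that out.

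**2. Is the removal one-sided?** Failure for intolerance applies to both arms (sections 4.3 and 4.4). The liver disqualification names tolvaptan titration and run-in only. Figure 1 schedules AST and ALT at the end of run-in without distinguishing arms, so a metformin patient can show the same rise, but no disqualification follows.

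**3. Which follow-up applies?**

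| Source | What it gives |
|---|---|
| Section 11 | Anyone who discontinues in titration or run-in is a failure of that period: end-of-treatment visit, and a 7-day call for run-in failures (section 4 gives the call to both kinds) |
| Section 10.2 | Adverse events: 7 days if stopped before randomisation, 21 days if randomised. Creatinine to the scheduled end if off drug but not withdrawn |
| Section 11.2 | After permanent discontinuation following randomisation: all assessments to Month 24 |
| Section 4.5 | Visits expected to Month 24 whether or not drug is stopped (placed under the treatment period that starts on Day 0) |

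Section 11 is the more specific rule for these four weeks, so a site would most naturally take the short route. That conflicts with section 11.2, which speaks of any stop after randomisation, and with section 4.5.

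**4. How large is the effect on precision?** With 150 patients at 1:1 there are 75 per arm. The documents give no rate of liver rises, so I assume a fraction f of the tolvaptan arm from 1% to 10% and treat removed patients as contributing nothing.

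SE ratio = sqrt(1/75 + 1/n) / sqrt(2/75), with n = 75(1 - f)

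| f | Patients removed | SE ratio |
|---|---|---|
| 1% | 0.75 | 1.0025 |
| 2% | 1.5 | 1.0051 |
| 5% | 3.75 | 1.0131 |
| 10% | 7.5 | 1.0274 |

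The standard error rises by about 0.3% to 2.7%.

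**The case against.** Several points on the other side are sound.

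- Sites will probably read the instruction as a bar to entering the 24-month period, which is how section 4.8 treats tolerability. That settles whether the patient goes on with treatment. It does not settle whether follow-up ends after a week or at Month 24.
- Section 11 classifies by period and not by reason, so it is too strong to say that sites have no guidance. The guidance they have is the short route, and that is what conflicts with section 11.2.
- A stricter threshold for tolvaptan is a legitimate drug-specific safety choice. Section 10.6 gives metformin its own lactate rules. Those rules, however, work by dose reduction, suspension and re-challenge within the allocated arm, which is what the tolvaptan rule lacks.
- Few patients can trigger the rule. Figure 1 schedules no liver enzymes at the end of titration. The one routine test before Day 0 is at the end of run-in, and other testing is prompted by symptoms or by abnormal screening values.
- The truncated follow-up is not peculiar to liver cases. Every titration or run-in failure, in either arm, is already randomised and gets the same short follow-up. This stands, and the remedy should cover them all.

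**Conclusion.** The concern holds as an internal contradiction with limited consequence. The rule cannot be carried out as written. Its practical effect is to cut follow-up of allocated patients on a criterion that exists in one arm only, against an analysis that promises to include everyone randomised. It should be corrected, but it does not threaten power: the 0.3% to 2.7% rise in standard error rests on an assumed 1% to 10% rate, and the true number cannot be estimated from the documents.

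A reader might infer more than the text supports:

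- *That these patients are dropped from the analysis set.* No passage says so; section 12.3 keeps all randomised subjects. What is lost is their data.
- *That the comparison is biased in a known direction.* Nothing in the documents links an early liver rise to the eGFR slope, so neither direction nor size is shown.
- *That a patient could be randomised twice.* Section 10.5.1.1 allows rescreening without saying that the allocation is kept. Nothing provides for a second allocation and nothing bars it; it is an unlikely risk.
- *That safety reports are lost.* Sections 10.1.4 and 10.1.9 require events to be collected from consent or the first study procedure onward, so they are captured either way.

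**What to change.** - In sections 10.5.1.1 and 10.5.1.2, replace disqualification from randomisation or from the trial with stopping or interrupting drug under the original allocation. Keep the stricter tolvaptan threshold.
- In section 10.5.1.2, replace the timing relative to randomisation with a stated run-in test day, for example Day -7.
- Replace rescreening with restart of the same allocated drug, only if the cause is judged unrelated and the medical monitor approves. Write both conditions out: section 10.5.1.3 alone would let rises below its listed thresholds resume without them.
- State that each subject is randomised once.
- Correct the wording in sections 4.4, 4.8, 10.2 and 11 that places these weeks before randomisation.
- Follow all titration and run-in failures in both arms, liver-related or not, to Month 24 as in section 11.2 unless consent is withdrawn, and analyse them in the allocated arm.

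The cost is a protocol amendment, visits to Month 24 for a few extra patients, and loss of re-entry by rescreening. The causality and medical-monitor safeguards are kept.

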10.5.1.2 Repeated Liver Testing in Subjects with Abnormal Values at Screening

Subjects found to have liver laboratory abnormalities at screening or who have a history of non-ADPKD-related liver disease will require further evaluation. These subjects will need to have the special liver eCRF completed and additional testing will be required during screening (to confirm the stability of the abnormality) and during the tolvaptan run-in phase at least 1 week prior to randomization (to confirm eligibility for randomization).

Management of such subjects should be closely coordinated with the trial's Medical Monitor. In these subjects, further changes in liver test levels of > 2 x upper limit of their highest screening value at any point post-screening should prompt re-testing within 72 hours. Should such increase occur in the tolvaptan titration/run-in phase, the subject will be disqualified from trial.

10.5.1.3 Liver Test Abnormalities and Interruption/Discontinuation of Investigational Medicinal Product

Liver transaminase or bilirubin levels reaching or exceeding 2 x ULN that have an uncertain or rapidly increasing trajectory should prompt at least temporary IMP interruption. IMP should not be resumed until monitoring indicates abnormalities have resolved, are stable or are not rapidly increasing, and then only with an increased frequency of monitoring.

Subjects would not typically be allowed to resume treatment with IMP if they have:

- transaminase levels rise above 8 x ULN;
- transaminase levels are > 5 x ULN for more than 2 weeks; or
- concurrent elevations of transaminase > 3 x ULN and BT > 2 x ULN.

Subjects with these levels of abnormality may be re-challenged with IMP if abnormalities were adjudicated as having a < 50% likelihood of being related to IMP (per DILI network [DILIN] probability criteria) by the investigator and medical monitor.

All elevations will be assessed by the medical monitoring team. The subject must also be willing to comply with these monitoring measures, be informed of the potential risks, and consent to IMP re-challenge.

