5.3 Exclusion Criteria

1) Women of childbearing potential (WOCBP) who do not agree to practice 2 different methods of birth control or remain abstinent during the trial and for 30 days after the last

dose of IMP. If employing birth control, 2 of the following precautions must be used: vasectomy of partner, tubal ligation, vaginal diaphragm, intrauterine device, birth control implant, condom, or sponge with spermicide. Non-childbearing potential in women is defined as female subjects who are surgically sterile (ie, have undergone bilateral oophorectomy or hysterectomy) or female subjects who have been postmenopausal for at least 12 consecutive months.

2) Women who are breast-feeding and/or who have a positive pregnancy test result prior to receiving investigational medical product (IMP).

3) Treatment with acarbose, guar gum, cimetidin, phenprocoumon, oral anticoagulants, thrombolytic drugs, diuretics, ranolazin, cephalexin.

4) Evidence of active systemic or localized major infection at the time of screening.

5) Hepatic impairment or liver function abnormalities other than that expected for ADPKD with typical cystic liver disease during the screening period as defined by:

- AST O ALT >8x UNL
- AST O ALT >5x UNL >2 WEEKS
- AST O ALT >3x UNL E BT >2x UNL OR INR >1,5
- AST O ALT >3x UNL E SIGNS AND SYMPTOMS OF LIVER DAMAGE (fatigue, anorexy, nausea, vomiting, right hypocondrium pain, fever, jaundice, skin rash, itching)

6) Acute or chronic disease causing tissue hypoxia (e.g.: myocardial failure, severe arythmias, myocardial infarction, respiratory failure, liver failure, alcohol acute intoxication, alcoholism, dehydration).

7) Previously diagnosed diabetes already in treatment with other hypoglycemic drugs.

8) Ongoing breast feeding.

9) Use of any other investigational drug or treatment up to 4 weeks before enrollment and during the treatment phase.

10) Known hypersensitivity to metformin and its derivatives.

11) Psychiatric disorders and any condition that might prevent full comprehension of the purposes and risks of the study.

12) Malignancies within three years before enrolment in the study.

13) HIV, HBV, HCV infection.

14) Urinary tract obstruction.

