10.1.7 Intensity (Severity) Reporting and Attribution

For both serious and non-serious adverse events, the Investigator must determine both the intensity of the event and the relationship of the event to study drug administration.

Intensity for each adverse event will be determined by using Version 4.0 of the National Cancer Institute Common Terminology Criteria for Adverse Events (NCI CTCAE) as a guideline, wherever possible; a copy of the NCI-CTCAE Version 4.0 can be downloaded from the Cancer Therapy Evaluation Program (CTEP) home page (http://evs.nci.nih.gov/ftp1/CTCAE/About.html). In those cases where the NCI CTCAE does not apply, intensity should be defined according to the following criteria:

- Mild: Awareness of sign or symptom, but easily tolerated;
- Moderate: Discomfort enough to cause interference with normal daily activities;
- Severe: Inability to perform normal daily activities;
- Life Threatening Immediate risk of death from the reaction as it occurred.

Relationship to study drug administration will be determined as follows:

- **Not related**: An adverse event which is not related to the use of the drug;
- Unlikely/Doubtful:An adverse event for which an alternative explanation is more likely, e.g., concomitant drug(s), concomitant disease(s), or the relationship in time suggests that a causal relationship is unlikely;
- Possible: An adverse event which might be due to the use of the drug. An alternative explanation, e.g., concomitant drug(s), concomitant disease(s), is inconclusive. The relationship in time is reasonable; therefore, the causal relationship cannot be excluded;
- Probable: An adverse event which might be due to the use of the drug. The relationship in time is suggestive (e.g., confirmed by dechallenge). An alternative explanation is less likely, e.g., concomitant drug(s), concomitant disease(s);
- Definite/Very Likely: An adverse event which is listed as a possible adverse reaction and cannot be reasonably explained by an alternative explanation, e.g., concomitant drug(s), concomitant disease(s). The relationship in time is very suggestive (e.g., it is confirmed by dechallenge and rechallenge).

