10.1.8 Relationship of Adverse Event to Investigational Product

The assessment of the relationship of an adverse event to the administration of study drug is a clinical decision based on all available information at the time of the completion of the CRF.

An assessment of 'No' would include:

1. The existence of a clear alternative explanation (e.g., mechanical bleeding at surgical site) OR

 Non-Plausibility (e.g., the subject is struck by an automobile when there is no indication that the drug caused disorientation that may have caused the event; cancer developing a few days after the first drug administration).

An assessment of 'Yes' indicates that there is a reasonable suspicion that the adverse event is associated with the use of the investigational drug. Factors to be considered in assessing the relationship of the adverse event to study drug include:

- The temporal sequence from drug administration: the event should occur after the drug is given. The length of time from drug exposure to event should be evaluated in the clinical context of the event.
- 2. Recovery on discontinuation (de-challenge), recurrence on reintroduction (rechallenge):

Subject's response after drug discontinuation (de-challenge) or subjects response after drug re-introduction (re-challenge) should be considered in the view of the usual clinical course of the event in question.

- Underlying, concomitant, intercurrent diseases: each report should be evaluated in the context of the natural history and course of the disease being treated and any other disease the subject may have;
- Concomitant medication or treatment: The other drugs the subject is taking or the treatment the subject receives should be examined to determine whether any of them may be suspected to cause the event in question;
- The pharmacology and pharmacokinetics (PK) of the test drug: The PK properties (absorption, distribution, metabolism and excretion) of the test drug(s), coupled with the individual subject's pharmacodynamics should be considered.

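### The joint causality adjudication before liver re-challenge (section 10.5.1.3) covers three laboratory patterns and leaves out two that exclude a patient at entry

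*Combined protocol and SAP*

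**What the plan says.** Section 10.5.1.3 asks for at least a temporary interruption when transaminase or bilirubin reaches 2 x ULN on an uncertain or fast-rising course. The general condition for restart is that "IMP should not be resumed until monitoring indicates abnormalities have resolved, are stable or are not rapidly increasing", followed by closer monitoring.

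The section then names three patterns after which restart is not typical: transaminase above 8 x ULN; above 5 x ULN for more than 2 weeks; and "concurrent elevations of transaminase > 3 x ULN and BT > 2 x ULN". For those three it provides: "Subjects with these levels of abnormality may be re-challenged with IMP if abnormalities were adjudicated as having a < 50% likelihood" of a relation to the drug, on DILIN criteria, with the investigator and the medical monitor both judging. It adds that "All elevations will be assessed by the medical monitoring team", and that the patient must be told the risks and agree to re-challenge.

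Exclusion criterion 5 (section 5.3, and the synopsis) uses the same cut-offs. Its bilirubin bullet carries an INR limb, "AST O ALT >3x UNL E BT >2x UNL OR INR >1,5", and a further bullet reads "AST O ALT >3x UNL E SIGNS AND SYMPTOMS OF LIVER DAMAGE". The Italian connectives O and E stand for or and and.

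In Figure 1, PT INR is a group of its own (EXAMS B), marked at the first screening visit.

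**The concern.** The adjudication rule is the only place where restart during the on-treatment period depends on a judged probability that the drug caused the injury. It applies to the listed levels only, and all three are laboratory values, although section 10.5 is headed as covering liver symptoms and signs as well.

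Suppose a patient has transaminase above 3 x ULN with an INR above 1.5, or with symptoms of liver damage, but bilirubin not above 2 x ULN. That patient meets a weaker written check at restart than a symptom-free patient with transaminase above 3 x and bilirubin above 2 x. Yet the protocol treats clinical signs of drug-induced liver injury as a serious adverse event (section 10.1.3) and would have excluded either patient at entry. What is at stake is the safety of re-exposure, in a trial whose secondary objectives (section 3.2) name acute liver injury as an event of interest.

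**Working it through.** No power or alpha calculation applies. The check sets the sections side by side.

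**Step 1. Entry patterns against restart patterns.**

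| Pattern | Exclusion 5 | Adjudication rule, 10.5.1.3 |
|---|---|---|
| Transaminase > 8 x | yes | yes |
| Transaminase > 5 x for > 2 weeks | yes | yes |
| Transaminase > 3 x with bilirubin > 2 x | yes | yes |
| INR > 1.5 limb | yes | no |
| Transaminase > 3 x with signs and symptoms | yes | no |

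The INR bullet can be read as > 3 x with (bilirubin > 2 x or INR > 1.5), or as (> 3 x with bilirubin > 2 x) or INR > 1.5 alone. Either reading gives 5 entry patterns, and 5 - 3 = 2 are not carried over.

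**Step 2. What still applies to the two omitted patterns.**

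| Safeguard | Section | Does restart depend on causality? |
|---|---|---|
| Values resolved, stable or not rapidly rising; then closer monitoring | 10.5.1.3 | No; it looks at the course of the values |
| Medical monitoring team assesses every elevation | 10.5.1.3 | No threshold given |
| Patient informed and consents to re-challenge | 10.5.1.3 | No |
| Investigator grades relatedness, weighing de-challenge and re-challenge | 10.1.7, 10.1.8 | Graded, but no grade bars restart |
| Clinical signs of drug-induced liver injury are an SAE, followed to baseline, normal or an explanation | 10.1.3, 10.2 | No |
| Hepatic function tested within 72 hours of a suspicious symptom | 10.5.1.1 | No |
| Possible stop for a drug-related safety concern (1.b) or clinical signs of liver injury (1.i) | 11 | A reason to stop, with no liver-specific restart condition |
| Rescreening after a rise in tolvaptan titration or run-in, if the cause is unrelated and the medical monitor approves | 10.5.1.1 | Yes, but for rescreening only |

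The last row is the one other place where causality governs a return to drug. It does not reach the 24-month on-treatment period.

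**Step 3. INR after screening.** Figure 1 has 2 screening columns, end of titration, end of run-in, 8 three-monthly visits and 2 follow-up visits: 2 + 1 + 1 + 8 + 2 = 14. PT INR is marked at 1 of them. AST, ALT and bilirubin (EXAMS C) are marked at 1 + 1 + 8 + 2 = 12. A stray mark in the INR row also appears in the rows for EXAMS G and height, and is read as a conversion artefact. INR is named in exclusion 5 (synopsis and section 5.3) and in the Figure 1 legend, and nowhere in sections 9 to 11.

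**The case against.** Entry and restart criteria serve different purposes and need not match. That is right as a principle, and mismatch alone would not be a fault. Here, though, 10.5.1.3 repeats three of the entry patterns at identical cut-offs, and the protocol gives no reason for stopping short of the other two.

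The list is also soft: it describes what is typical and is not an outright ban. And the gap is narrower than the count suggests. A symptomatic or INR-raised patient who also meets one of the three listed patterns is already covered; some jaundiced patients may qualify through bilirubin. Both points stand, and both lower the weight of the finding.

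INR could be ordered as part of the hepatic function testing in 10.5.1.1, the liver function tests in 9.1.4 or the liver panels in 10.3. Figure 1 is not a complete list in any case, since it omits the alkaline phosphatase that 10.5 requires at screening. This stands too: the protocol permits INR after screening but does not ensure it.

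Finally, section 2.2 says tolvaptan is used under its marketing authorisation. The liver terms of that authorisation are not in the documents, so whether they close the gap in that arm cannot be checked. They would not cover metformin.

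**Conclusion.** The point holds as a minor patient-safety gap in wording. During the on-treatment period, two of the five liver patterns that bar entry have no causality threshold before restart when none of the three listed patterns is also present. The number of such patients cannot be derived. The conclusion rests on taking the levels referred to in the re-challenge sentence as the three bullets directly above it.

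Several stronger readings are not supported:

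- *Restart is unregulated, or causality is never assessed, for these patients.* The safeguards in Step 2 apply, and section 10.1.7 says that "the Investigator must determine both the intensity of the event and the relationship of the event to study drug administration". What is missing is a threshold that binds restart.
- *The resumption sentence permits restart once values settle.* It states a necessary condition, not a sufficient one.
- *INR is never measured after screening.* It is neither scheduled nor named, which is a weaker statement.
- *In the tolvaptan arm the gap opens only after run-in, because any rise above 2 x ULN before then disqualifies.* That rule is for patients with normal screening values. Under 10.5.1.2 the limit is twice the highest screening value: a patient screened at 1.9 x ULN has a limit of 2 x 1.9 = 3.8 x ULN, so a rise to 3.5 x would not disqualify. No share of treatment time should therefore be attached to the gap.
- *The gap biases an endpoint or the arm comparison.* Nothing in the documents shows this, and it is not claimed.

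**What to change.** Add two patterns to the 10.5.1.3 list: *transaminase > 3 x ULN with INR > 1.5*, and *transaminase > 3 x ULN with new signs or symptoms of liver damage*. Both would then need the joint adjudication below 50% before re-challenge. Neither becomes an automatic permanent stop. Any alternative cause for the symptoms should be weighed inside that adjudication. If it were made a condition for entering it, one unadjudicated opinion could bypass the step.

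Cross-reference section 11 items 1.h and 1.i to the extended list, and name INR in the 72-hour re-tests of both 10.5.1.1 and 10.5.1.2. If the sponsor means INR above 1.5 alone to exclude at entry, an isolated INR rise would still fall outside this wording, and the sponsor should say whether that is intended.

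The cost is a few lines of protocol text, one extra assay on re-test samples, and some additional adjudications, because several of the listed symptoms (fatigue, nausea, fever) are non-specific.
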